9.5.2. Secondary Analyses

Durability of rTMS effects (Aim 2a)

- Analysis: Longitudinal analysis of primary efficacy measure (memory performance) over the entire trial period in relation to treatment group
- Method: Mixed-effects growth curve modeling
- Population: ITT
- Dependent variable: CVLT-II Trials 1-5 Total raw score (Visits 2, 13, 14,15)
- Independent variable: rTMS Treatment group
 - Model 1: active DLPFC vs sham
 - Model 2: active LPC vs sham
- Results: Mixed model parameters with estimates will be provided.

- Contrasts: To convey the durability of the effect of each type of rTMS stimulation on the primary efficacy measure, the magnitude of treatment effects at the 3-mos and 6-mos time points will be reported.

Analysis of behavioral differences related to stimulation site (Aim 2b.1)

- Analysis: Longitudinal analysis of behavioral changes over the entire trial period in relation to treatment group.
- Method: Mixed-effects growth curve modeling.
- Population: ITT.
- Dependent variables: Behavioral measures listed in Section 9.4.2.a (Visits 2, 13, 14 & 15). Semantic clustering and delayed recall sub-scores of the CVLT-II are of most interest.
- Independent variable: Active rTMS Treatment group (DLPFC vs LPC).
- Results: Mixed model parameters with estimates will be provided.

Analysis of effects on brain function related to stimulation site (Aim 2b.2)

As noted above, rs-fMRI data will be acquired at baseline (Visit 2) and post-intervention (Visit 13) to examine effects of rTMS on brain function. Secondly, plasma levels of brain-derived neurotrophic factor (BDNF) will be measured at the first and last intervention sessions to gain information about mechanisms of action of rTMS with respect to brain plasticity.

BDNF levels analysis (two time-points). As in the primary analysis, ANCOVA will be used.

Functional connectivity (two time-points).

- To define the DMN and CEN networks, we will perform seed-based whole brain analysis of the baseline fMRI data, using the methods of Greicius (for the DMN) and Vincent (for the CEN). The networks will be broadly defined ($p < .01$) from the group data to generate inclusive masks of the DMN and CEN.
- 1) Analysis of rTMS effects on PCC connectivity within the DMN. As described in more detail in Appendix VIII, connectivity maps will be calculated by the correlating subject's timeseries of the PCC seed-ROI with those of non-seed voxels in the DMN group mask, followed by Fisher's r to z transform of the values. Contrasts of the connectivity maps will be made (Pre- vs. Post-Tx, for each active rTMS vs. sham, and for active LPC vs. DLPFC). The aim of these analyses is to discover the extent to which rTMS restores connectivity of the PCC within regions of the DMN. rTMS-induced increases in PCC:hippocampal, PCC:parahippocampal, PCC:LPC, and/or PCC:mPFC connectivity would provide indications of therapeutic response (J. X. Wang et al., 2014; J. X. Wang & Voss, 2015; Ward et al., 2014).
- Analysis of rTMS effects on between-network connectivity. As explained in Appendix VIII, we will define 6 *a priori* ROIs: bilateral PCC (posterior DMN), and DLPFC (key node of the CEN) and medial PFC (anterior DMN). For each subject and scan session, a correlation matrix of ROI-pairwise timeseries correlations will be computed; next, each participant's z -score matrix (using Fisher's r -to- z transform) will be used to compute Pre-minus-Post changes in z values. These will be used in group-level analyses to compare each active rTMS to sham-control and

to compare active LPC to DLPFC. The aim of these analyses is to examine the extent to which rTMS reduces functional connectivity between the DMN and CEN. Decreases in PCC:DLPFC and mPFC:DLPFC between-network connectivity would provide indications of therapeutic response.

- Finally, we will explore the extent to which rTMS-induced changes in functional connectivity correlate with changes in selected behavioral variables (delayed recall, semantic clustering, executive function, and depression).

Heterogeneity of response to rTMS (Moderators: Aim 2c).

To explore the extent to which one treatment is superior over another as a function of a moderator variable, we will fit regression models with interactions between the treatment group variable and a selected moderator variable, yielding estimates of the regression line for each group. In addition to reporting the magnitude of the interaction as a p value, we will obtain predicted values of the regression lines corresponding to each group. (From these, we can estimate the superiority of one treatment over another as a function of the moderator; confidence intervals and p-values can be readily reported). As these are exploratory analyses, we would analyze individual moderators separately to avoid over-fitting the models.

Based on limited data from previous TMS studies, the following classes of moderators are most likely to account for heterogeneity of response to rTMS in patients with MCI:

- Profiles of baseline cognitive deficits, as defined by CVLT-II clustering and delayed recall scores;
- Brain endophenotypes, as defined by a baseline functional connectivity metric for the Language, Central Executive, and Default-mode Networks;
- BDNF met carrier status (in other clinical populations, val/val genotype has predicted a better response to rTMS (Chang et al., 2014; Cheeran et al., 2008)).

In addition, gender and racial/ethnic categorical variables will be examined to gauge the magnitude of any potential differences in response to rTMS in patients with MCI.

Descriptive analyses of safety and tolerability

Adverse events will be coded according to established Medical Dictionary for Regulatory Activities (MedDRA) terms and summarized by MedDRA System Organ Class and Preferred Term. In most cases, aggregate safety and tolerability data (see Section 7.2) will be summarized with descriptive statistics (counts, percentages, mean and standard deviation) for all participants, by treatment group and by study phase (i.e., intervention and follow-up). Summaries will indicate whether events were determined to be related to the study device and whether the AE led to treatment discontinuation. Inferential comparisons may include t-tests or chi-square tests as appropriate. The time course of incidence of common treatment-related adverse effects will be examined to characterize the extent to which participants accommodated to the treatment.

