1.2 Secondary Objectives

- (2a) **Assess the durability** of rTMS effects. To address Objective 2a, we will assess the extent to which rTMS-related improvements in memory are sustained at the 3- and 6-month follow-up points
- (2b) **Examine effects related to the site of stimulation** (DLPFC vs LPC). To quantify effects of rTMS treatment, MCI-relevant behavioral measures and resting-state functional MRI (rs-fMRI, aka task-free fMRI) data will be collected.
 - 2.b.1. One set of analyses will be done to examine differences in behavioral outcomes related to the site of rTMS stimulation.
 - 2.b.2. The second set of analyses will focus on indices of improved brain functional connectivity (derived from rs-fMRI) and plasticity (assessed by levels of BDNF).
- (2c) **Explore patient characteristics** that could be useful in identifying who responds preferentially to rTMS or to a particular stimulation site. To address Objective 2c, regarding heterogeneity of response to rTMS, baseline functional connectivity, genetic, and selected clinico-demographic variables will be explored as potential moderators of response to rTMS.

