- Montreal Cognitive Assessment (MoCA; (Nasreddine et al., 2005));
- CVLT-II; (Delis et al., 2000) selected subscores: semantic clustering, short-delay free recall; long-delay free recall, and recognition discriminability
- Brief Visuospatial Memory Test-Revised (BVMT-R) (Benedict, Schretlen, Groninger, Dobraski, & Sphritz, 1996)

- Rey-Osterrieth Complex Figure (ROCF). Copy task only (2 stimulus forms: original ROCF form and modified Taylor figure (Hubley, 2010; Hubley & Jassal, 2006);
- Category Fluency (Strauss, Sherman, & Spreen, 2006)
- Boston Naming Test (BNT) (Huff et al. (1986) two-equivalent forms version)
- Trail Making (Partington & Leiter, 1949; Reitan, 1958)
- Attentional Network Task (ANT) (Fan, McCandliss, Sommer, Raz, & Posner, 2002; Posner, 2012; Y.-F. Wang et al., 2015),

(Note: Except for Fluency and Trail Making tests, all tests have validated alternate stimulus forms, in order to reduce the magnitude of practice effects. Fluency and Trails are included because they are widely used tests, and their brevity should not add substantial participant burden.)

Secondary fMRI and BDNF measures relevant to improved functional connectivity and plasticity. Resting-state fMRI (rs-fMRI, aka task-free fMRI) scans will be acquired at the Baseline and Immediate post-treatment visits to examine effects of rTMS on functional connectivity. Additionally, plasma levels of brain-derived neurotrophic factor (BDNF) will be measured before and at completion of treatment as a strategy to gain more information about mechanisms of action. BDNF expression in the brain plays a role in synaptic remodeling (McAllister, Katz, & Lo, 1999). It has been suggested that the longer-lasting effects of rTMS involve long-term potentiation-like (LTP-like) mechanisms (Hoogendam, Ramakers, & Di Lazzaro, 2010). Although a direct link between neuromodulatory stimulation, such as rTMS, and synaptic plasticity remains to be demonstrated, an rTMS-related rise in BDNF plasma levels would be consistent with an effect on brain plasticity.

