9 STATISTICAL CONSIDERATIONS

9.1 General Design Issues

This is a double-blind, randomized, 2-stimulation-site, sham-controlled parallel group design of rTMS treatment to either bilateral DLPFC or LPC. The parallel groups design avoids potential carryover effects of active rTMS treatment to other treatment conditions within the same subject. The length of an appropriate washout period for rTMS has not been established for this rTMS intervention protocol in this population.

Primary Hypothesis

The primary hypothesis is that participants receiving active (“real”) rTMS will show more improvement in memory at the immediate post-treatment assessment than the placebo (sham) control group. The sham group is comprised of all subjects assigned to the sham group, regardless of the position of the sham coil.

Testing the primary hypothesis involves two statistical tests: Test 1 will compare Active DLPFC to sham; Test 2 will compare Active LPC to sham.

For these tests, memory is measured by the CVLT-II Trials 1-5 Total raw score. This outcome measure has excellent retest reliability (Total and Delayed: $r > .75$), diagnostic validity (Rabin et al., 2009) (Silva et al., 2012), and normative data on a representative sample. The CVLT, which is comprised of 16 concrete words presented for 5 learning trials, helps achieve a wide range of scores that are neither at floor nor at ceiling level (Ellis et al., 2009; Karrasch, Sinerva, Gronholm, Rinne, & Laine, 2005; Ribeiro, de Mendonca, & Guerreiro, 2006). An additional advantage of the CVLT-II is the availability of alternate test forms.

Secondary Analyses

This study, was originally proposed in response to NIH/NIA PAR-16-365 “Pilot Clinical Trials for the Spectrum of Alzheimer’s Disease and Age-related Cognitive Decline (R01).” In addition to testing the primary hypothesis to learn whether rTMS is a viable nonpharmacological intervention for treatment of MCI, this study was designed to address essential questions of durability, choice of site, and prediction of response. Information gained from this study will inform efforts to optimize rTMS effectiveness and pave the way for further clinical development. From this perspective, we plan to examine durability of rTMS over the 6-month follow-up, and to describe effects of rTMS on secondary cognitive and behavioral outcomes, as described below:

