(Grant Aim 2a) Assess the durability of rTMS effects: The primary efficacy measure, the CVLT-II Trials 1-5 Total raw score will be analyzed for effects of rTMS on memory at 3- and 6-month post-intervention. Our working hypothesis is that an effect of rTMS on memory will be sustained up to 3 months.

(Grant Aim 2b.1) Examine behavioral differences related to the site of brain stimulation: The secondary behavioral outcomes will be analyzed in longitudinal data analyses with respect to the site of active stimulation (DLPFC or LPC). The secondary behavioral outcomes of most interest are selected sub-scores of the CVLT-II.

- Because the DLPFC and LPC have distinct roles in memory encoding and delayed recall (Long, Oztekin, & Badre, 2010), our working hypothesis is that DLPFC stimulation could result in a higher level of semantic clustering compared to LPC

stimulation. By contrast, LPC stimulation could result in higher recall, assessed by CVLT-II short- and long-delayed recall scores. An rTMS-induced increase in semantic clustering would be a positive outcome in MCI because older adults who showed more semantic clustering on the CVLT-II were more cognitively stable over time (McLaughlin et al., 2014). An rTMS induced increase in delayed recall would also be clinically important.

As part of addressing secondary Aim 2b.1, effects of rTMS on other secondary outcomes will be described. These outcomes include depressive symptoms, objective assessments of global cognitive function, visuospatial episodic memory, language, visuo-constructional ability, orienting of attention, information processing speed, executive function, and self-/partner-reported assessments of everyday cognitive functioning. All measures have demonstrated re-test reliability and construct validity. These secondary outcomes (which are described in Section 6.2.2) are listed in Section 9.4.2 below.

(Grant Aim 2b.2) Changes in brain function related to the site of brain stimulation.

This study is designed to provide novel information about the therapeutic mechanisms of rTMS in the target population. Resting-state fMRI scans will be acquired at the Baseline visit and the Immediate Post-Treatment visit to examine effects of rTMS on brain functional connectivity. Additionally, plasma levels of brain-derived neurotrophic factor (BDNF) will be measured before and at completion of the rTMS intervention.

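### The secondary behavioural outcomes in Section 9.4.2.a have no specified comparison with sham, and the list omits the long-delay recall that the Aim 2b.1 hypothesis names

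*Combined protocol and SAP*

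**What the plan says.** For Aim 2b.1, Section 9.5.2 specifies mixed-effects growth curves in the ITT population. The dependent variables are the measures listed in Section 9.4.2.a at Visits 2, 13, 14 and 15. The comparison is "Independent variable: Active rTMS Treatment group (DLPFC vs LPC".

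Section 9.1 promises more than a site comparison. Its introduction to the secondary analyses plans "to describe effects of rTMS on secondary cognitive and behavioral outcomes", and its Aim 2b.1 text says that "effects of rTMS on other secondary outcomes will be described". Section 1.2 gives a similar purpose, "To quantify effects of rTMS treatment, MCI-relevant behavioral measures and resting-state functional MRI", although that sentence stands under the site objective.

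For functional connectivity, Section 9.5.2 writes out the full set of contrasts: "for each active rTMS vs. sham, and for active LPC vs. DLPFC".

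On recall, the Aim 2b.1 hypothesis in Section 9.1 is that "LPC stimulation could result in higher recall, assessed by CVLT-II short- and long-delayed recall scores". Section 3 lists the secondary CVLT-II subscores as "semantic clustering, short-delay free recall; long-delay free recall, and recognition discriminability". Section 9.4.2.a lists only semantic clustering and short-delay free recall.

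**The concern.** A contrast between two active arms estimates the difference between sites. It carries no information about an effect that both sites share. The growth curves will show how each active arm moves over time, but not how much of that movement rTMS caused.

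The protocol itself expects practice effects at repeated testing. Section 3 says: "Except for Fluency and Trail Making tests, all tests have validated alternate stimulus forms, in order to reduce the magnitude of practice effects". Fluency and Trail Making Part B are both in Section 9.4.2.a.

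At stake is the interpretation of depressive symptoms, everyday function, global cognition, clustering and recall. Section 9.1 would count an rTMS-induced rise in semantic clustering as a favourable result, but the specified model cannot show that a rise was rTMS-induced. If the sham comparison is not written down beforehand, whether and how to make it for each outcome is decided after the data are seen.

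**Working it through.** The plan states no figure on this point, so the check is of the text first, then of what the specified contrast can detect.

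**1. Where a sham comparison is written**

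| Outcome | Place | Sham comparison |
|---|---|---|
| CVLT-II Trials 1-5 Total, Visit 13 | 9.5.1 | Yes, each active arm |
| CVLT-II Trials 1-5 Total, all visits | 9.5.2, Aim 2a | Yes, each active arm |
| Functional connectivity | 9.5.2, Aim 2b.2 | Yes, plus LPC vs DLPFC |
| BDNF | 9.1 hypothesis; ANCOVA in 9.5.2 | Hypothesis framed against sham |
| Measures in 9.4.2.a | 9.5.2, Aim 2b.1 | None |

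The moderator models of Aim 2c name neither the groups compared nor the outcome, so they do not fill the gap.

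**2. Count of scores.** Section 9.4.2.a lists GDS, ECog (counted as one total), FAQ, MoCA, semantic clustering, short-delay recall, BVMT-R, Category Fluency, Boston Naming, ROCF copy, Trail Making B and three Attentional Network Task scores: 14. Appendix XI drops that task: 14 - 3 = 11. Scores with a specified sham contrast: 0 of 11. Scores from tests without alternate forms: 2 of 11.

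**3. Two cases the plan cannot tell apart.** The 0.5 SD is illustrative.

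| | Case A: practice gain 0.5 SD in all arms, no rTMS effect | Case B: no practice gain, rTMS gain 0.5 SD at both sites |
|---|---|---|
| Change from baseline, each active arm | 0.5 SD | 0.5 SD |
| DLPFC minus LPC | 0.5 - 0.5 = 0 | 0.5 - 0.5 = 0 |
| Active minus sham | 0.5 - 0.5 = 0 | 0.5 - 0 = 0.5 SD |

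A simulation of 4,000 trials per case (33 per arm, baseline-adjusted three-arm model at one visit) agrees. The mean DLPFC-LPC contrast was 0.00 in both cases, with 5% of tests significant. The mean DLPFC-sham contrast was 0.00 in A and 0.50 in B. In B it was significant at 5% in 64% of trials with baseline correlation 0.5 and in 85% with 0.75.

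**4. Precision of the missing contrast.** Inputs: 33 per arm (Précis); baseline-outcome correlation r of 0.5 or 0.75. The correlations are assumptions: Section 9.1 gives a retest reliability above .75 for CVLT Total and Delayed only.

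- SE = sqrt(2/33) × sqrt(1 - r²), in SD units.
- r = 0.5: 0.2462 × 0.8660 = 0.213; times t(95 df) = 1.985 gives 0.42 SD.
- r = 0.75: 0.2462 × 0.6614 = 0.163; times 1.985 gives 0.32 SD.
- With 31 per arm (33 × 0.94, the 6% attrition cited in Section 9.2): sqrt(2/31) = 0.2540 and t(89 df) = 1.987. The half-widths become 0.2540 × 0.8660 × 1.987 = 0.44 SD and 0.2540 × 0.6614 × 1.987 = 0.33 SD.

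**5. Recall list.** Long-delay free recall appears in the Section 9.1 hypothesis, in Section 3 and in the baseline test order of Section 6.2.2. Baseline assessments are repeated at Visit 13, and the cognitive battery is given again at Visits 14 and 15 (Section 6.2.4, Table 2). It is missing only from Section 9.4.2.a, the list that Section 9.5.2 turns into dependent variables. Recognition discriminability, named in Section 3, is missing in the same way.

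**6. Executive function (lesser point).** Section 9.5.2 correlates connectivity change with executive function. The only outcome filed under that heading in Section 9.4.2 was an Attentional Network Task score. Trail Making B is filed under speed of processing, so no measure is now named for this correlation.

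**The case against.** The strongest reply is that sham is implied. The Aim 2b.1 block opens by relating behavioural change to treatment group, and Section 4.3 defines three treatment groups for the data analyses, sham included. But the independent-variable line in the same block narrows this to the two active arms. Aim 2a opens in similar terms and then does write out its sham models.

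Second, Section 9.1 promises only description, in a study presented as a pilot, and the Section 1.2 sentence belongs to the site objective. The remark on Section 1.2 is fair, and the point does not rest on that sentence. The two statements in Section 9.1 are enough, because a description of rTMS effects needs a comparator and none is given.

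Third, the sham arm has these outcomes at the same visits, so the data can separate rTMS from practice. Measures, visits, population and model type are fixed, and Aim 2a offers a template. All of this is true. The gap is in the stated analysis, not in the design or data, which limits its weight and makes it cheap to close.

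Fourth, the numerical cases follow by construction, and the intervals come from a single-visit model rather than a growth curve. That also stands: they show the size of what is missing and are not forecasts.

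Finally, the recall list and the executive-function measure are matters of reconciliation. Dropping the Attentional Network Task by appended amendment is the route the protocol prescribes and is no error in itself.

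**Conclusion.** The concern holds. As written, the plan gives no active-versus-sham estimate for any of the 11 remaining scores in Section 9.4.2.a. It therefore cannot separate an rTMS effect common to both sites from practice or placebo response on those outcomes. The list of dependent variables also omits a recall score that the Aim 2b.1 hypothesis names and the trial collects.

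This should be fixed, but it is confined to secondary behavioural outcomes. The primary analysis, the Aim 2a durability analysis and the site comparison are not affected. The textual finding needs no assumption. The half-widths of 0.42 and 0.32 SD rest on 33 per arm with complete data and on the assumed correlations of 0.5 and 0.75; 6% attrition changes them little.

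**What to change.** In Section 9.5.2, Aim 2b.1:

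- Fit one three-arm mixed model per Section 9.4.2.a outcome. Report DLPFC minus sham and LPC minus sham at Visits 13, 14 and 15 with 95% confidence intervals. Keep DLPFC minus LPC as the site contrast.
- Label the sham contrasts secondary and descriptive, with no efficacy claim drawn from them, or state a multiplicity rule.

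In Section 9.4.2.a:

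- Add CVLT-II long-delay free recall.
- State whether recognition discriminability is an outcome.

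In Section 9.5.2, Aim 2b.2, name the retained executive-function measure for the exploratory correlation, for example Trail Making Part B.

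The cost is SAP wording; no new patients or data are needed. The drawback is multiplicity. With long-delay recall there are 11 + 1 = 12 outcomes, so 12 × 2 = 24 sham contrasts per visit and 24 × 3 = 72 over three visits. Unadjusted at 5% and with no true effects, 24 × 0.05 = 1.2 per visit, or 72 × 0.05 = 3.6 in all, would be expected to reach nominal significance. Analysing the self and partner ECog versions separately raises the per-visit count to 13 × 2 = 26, and recognition discriminability would add 2 more. Hence the descriptive label or the multiplicity rule.

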- (2c) Explore patient characteristics that could be useful in identifying who responds preferentially to rTMS or to a particular stimulation site.

Design and Primary Outcome

The study will use a double-blind, placebo (sham)-controlled, randomized 3-arm design.

Different cortical stimulation-sites will be studied in the two Active arms:

- Active group 1: Bilateral dorsolateral prefrontal cortex (DLPFC);
- Active group 2: Bilateral Lateral Parietal cortex (LPC)

Primary Outcome is the California Verbal Learning Test (CVLT-II) Trials 1-5 Total raw score

Interventions and Duration

Participants will be randomly assigned to one of **three treatment groups**: Group 1: DLPFC Active rTMS; Group 2: LPC Active rTMS; and Group 3: Placebo (sham) control (evenly split between each coil location). Thus, a participant has a 2/3 chance of receiving active rTMS.

Each participant will participate in the study for approximately 7 ½ months—including a daily rTMS treatment phase (20 sessions in all), and post-intervention follow-up lasting 6-months.

Sample Size and Population

Sample Size: 99 men and women between the ages of 55 and 90 inclusive (n=33 per group).

Target population: Individuals with a clinical diagnosis of single- or multi-domain amnestic MCI (aMCI). MCI is an intermediate state between normal aging and dementia due to conditions such as Alzheimer’s disease (AD).

STUDY TEAM ROSTER

Principal Investigator: **[name].**

VA Palo Alto Health Care System (151Y)
[name]
[name]
Voice: [contact] [name]
[contact]
email: [contact] and [contact]

Co-Investigators:

[name] [name] (Psychiatry; Alzheimer's Disease)

VA Palo Alto Health Care System (151Y)
[name]
[name]
Voice: [contact] [name]
[contact]
e-mail: [contact] and [contact]

[name] [name] (Mechanisms of TMS)

VA Palo Alto Health Care System (151Y)
[name]
[name]
Voice: [contact] [name]
[contact]
email: [contact]

[name] (Biostatistician)

Department of Psychiatry & Behavioral Sciences
Stanford University School of Medicine
[name]
[name]
Voice: [contact]
[contact]
email: [contact]

[name] (rTMS Brain Injury Rehabilitation)

VA Palo Alto Health Care System (PSC/117)
[name]
[name]
Voice: [contact] [name]
[contact]
email: [contact] and [contact]

Other Significant Contributors

([name]) [name], PhD (rTMS-Dementia)

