9.2 Sample Size and Randomization

Power to test the primary hypothesis. We have powered the proposed study to detect a moderately large effect size (Cohen's $d = 0.80$) of either rTMS treatment on the primary outcome. Moderately large effect sizes of 1.0, 0.80, and 0.80 were reported in two meta-analyses of rTMS studies in AD (Liao et al., 2015) (Hsu et al., 2015) and one rTMS trial in MCI (which used unilateral rTMS (Drumond Marra et al., 2015), deemed suboptimal by (Liao et al., 2015)). Our proposed design is estimated to have 80% power to detect an effect size of 0.8, for a 5% two-tailed test, with a multiple testing penalty for 2 tests.

Attrition and the test of the primary hypothesis. The attrition rate in [name] rTMS TBI trial at our site has been 0% so far. The rate of attrition in the rTMS MCI trial (Drumond Marra et al., 2015) due to all reasons was 6%. Based on these rates of attrition, we do not expect attrition to substantially reduce power or the interpretation of results. If a participant in the present study discontinues the intervention early, we will encourage the participant to undergo all post-intervention assessments that are normally administered during the Follow-up Phase (Visits 13, 14, and 15). If there are baselined participants who have missing outcome data, we will perform and report sensitivity analyses that include participants with missing data, and make plausible assumptions about their outcomes based on the observed data. Additionally, the total minutes of rTMS received by each participant can be used as a covariate in the data analyses.

Attrition and secondary data analysis of behavioral outcomes. For the durability analysis of rTMS effects, mixed-effect growth curve analyses will be used, which enables full utilization of repeatedly measured outcomes and minimizes bias if subjects drop out during the extended follow-up period of the study (Singer & Willett, 2003).

Likelihood of obtaining other useful secondary results. In these secondary analyses, the proposed sample size will provide 80% power to detect a large difference ($d = 1.00$) related to the site of stimulation. For all analyses, we will convey practical significance by reporting effect sizes and confidence intervals, in addition to reporting statistical significance.

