9.5 Data Analyses

9.5.1. Primary Hypothesis Testing

- Analysis: Test the hypothesis that active rTMS (to either stimulation site) is superior to sham in improving memory performance, as observed at the immediate post-treatment visit.
- Method: Analysis of Covariance (ANCOVA)
- Population: Intention-to-treat (ITT), defined as all randomized patients who started at least 1 treatment session.
- Independent variable: rTMS Treatment group
 - ANCOVA 1: active DLPFC vs sham
 - ANCOVA 2: active LPC vs sham
- Dependent variable: Primary outcome, i.e. CVLT-II Trials 1-5 Total raw score at Visit 13
- Covariate: CVLT-II Trials 1-5 Total raw score at Baseline, i.e. Visit 2
- Results will be presented as n, mean and standard deviation of CVLT-II (Total Trials 1-5) scores at baseline and post-treatment. ANCOVA model parameters with estimates will be provided.
- The two tests of treatment effects will be conducted at a 2-sided alpha level of 0.05, adjusted for two tests; 2-sided confidence intervals will be displayed with a 95% confidence level.

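### Between-network connectivity is compared on pre-minus-post changes with no baseline covariate stated; adding the baseline value would sharpen the comparison at almost no cost

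*Combined protocol and SAP*

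**What the plan says.** Section 9.5.2, under Aim 2b.2, describes two connectivity analyses from the scans at Visits 2 and 13.

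- **Between networks.** Pairwise correlations among six regions are transformed to Fisher z, and each participant's z matrix "will be used to compute Pre-minus-Post changes in" z values. Then: "These will be used in group-level analyses to compare each active rTMS to sham-control and" to compare the two active sites with each other. No model is named and no covariate is listed. Detail is deferred: "As explained in Appendix VIII, we will define 6" regions.
- **PCC maps within the DMN.** The wording is looser: "Contrasts of the connectivity maps will be made (Pre- vs. Post-Tx, for each active rTMS vs. sham", and likewise for LPC against DLPFC. It does not say whether difference maps are the outcome or whether baseline is adjusted for.

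Other outcomes compared between one pre-treatment and one later measurement are handled differently. For BDNF, in the same aim: "BDNF levels analysis (two time-points). As in the primary analysis, ANCOVA will be used". For the primary outcome, Section 9.5.1 specifies: "Covariate: CVLT-II Trials 1-5 Total raw score at Baseline, i.e. Visit 2".

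**The concern.** A change score is an ANCOVA whose baseline slope has been set to 1 instead of estimated. When the true slope is below 1, which is usual for a measure with scan-to-scan noise, two things follow. The contrast carries variance that the baseline scan could have removed. It also over-corrects chance baseline differences: an arm that starts high tends to fall back, and that fall is counted in its change score.

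The plan reads decreases in PCC:DLPFC and mPFC:DLPFC connectivity as signs of therapeutic response, so extra noise in this contrast bears directly on how Aim 2b.2 is interpreted. Section 9.2.1 describes blocked randomisation with no stratification, so nothing in the design balances baseline connectivity. Sections 8.1 and 8.3 omit the Visit 13 MRI after discontinuation or withdrawal during the intervention, so fewer than 33 scans per arm may be available. The baseline z is already computed for every change score, so leaving it out of the model saves nothing.

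**Working it through.** **Inputs.** The sample is "99 men and women between the ages of 55 and 90 inclusive (n=33 per group" (Précis). The primary power statement is "80% power to detect an effect size of 0.8, for a 5% two-tailed test, with a multiple testing penalty for 2 tests" (Section 9.2). No power, precision or scan-rescan correlation is given for connectivity. The only retest figure, r above 0.75 in Section 9.1, concerns the CVLT-II and cannot be carried over. I therefore assume r from 0 to 0.9, with equal variance σ² at both scans.

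**The plan's own figure.** With d = 0.8 and a two-sided 0.025 per test (taking the penalty as Bonferroni), the noncentral t gives 31 per arm for 80.0% power. Allowing for the 6% attrition cited in Section 9.2, 31/0.94 = 32.98, hence 33. The stated size is reproduced. It concerns the primary outcome only.

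**Variances.** Per participant, in units of σ²:

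- change score: 2(1 − r)
- ANCOVA: 1 − r²
- ratio, ANCOVA to change: (1 − r²) / [2(1 − r)] = (1 + r)/2
- precision (inverse variance) lost by the change score: 1 − (1 + r)/2 = (1 − r)/2
- interval width, change relative to ANCOVA: √[2/(1 + r)]

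For r = 0.5, the variances are 1.00 and 0.75, the loss is 25%, and √(1/0.75) = 1.155, so intervals are 15.5% wider.

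Estimating the slope multiplies the ANCOVA variance by 1 + 1/(2n − 4), which is 63/62 = 1.016 at n = 33 per arm. The fourth column below includes this cost; the other columns do not.

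| r | Precision lost | Interval wider by | Lost after slope cost | ANCOVA per-arm n equal to 33 on change | Detectable difference, change / ANCOVA |
|---|---|---|---|---|---|
| 0 | 50% | 41.4% | 49.2% | about 17 | 0.98 / 0.69 |
| 0.3 | 35% | 24.0% | 34.0% | about 21 | 0.82 / 0.66 |
| 0.5 | 25% | 15.5% | 23.8% | about 25 | 0.69 / 0.60 |
| 0.7 | 15% | 8.5% | 13.6% | about 28 | 0.53 / 0.49 |
| 0.9 | 5% | 2.6% | 3.5% | about 31 | 0.31 / 0.30 |

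The fifth column is 33(1 + r)/2. The last column is in units of σ, for 80% power at a two-sided 0.05 on a single contrast with all 33 per arm (normal approximation). It illustrates scale and does not describe a planned test. A simulation of 8,000 trials at 33 per arm gave losses of 32%, 24% and 14% at r = 0.3, 0.5 and 0.7, close to the formula.

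**Direction without equal variances.** With standard deviations s₁ (pre) and s₂ (post), Var(change) − Var(ANCOVA) = s₁² + s₂² − 2r·s₁s₂ − s₂²(1 − r²) = (s₁ − r·s₂)², which is never negative. Under equal variances, the slope-estimation cost cancels the gain only when (1 + r)/2 = 62/63, that is r = 0.968.

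**Chance imbalance.** One standard error of the baseline difference is √(2/33) = 0.246σ. With no treatment effect, a baseline difference of that size moves the expected pre-minus-post contrast by (1 − r) × 0.246σ: 0.17σ, 0.12σ and 0.07σ at r = 0.3, 0.5 and 0.7. The shift goes in the direction of the baseline difference, which is over-correction.

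**The case against.** The strongest objection is that a change-score outcome does not by itself show that precision is lost. If change is regressed on group plus baseline z, the baseline coefficient shifts by 1, while the treatment estimate and its standard error match ANCOVA, apart from sign for pre-minus-post. Section 9.5.2 names no group-level model and defers to Appendix VIII, whose text is not in the document available to me. A reader might infer that the plan rejects baseline adjustment; the text does not say so. This stands, and it limits the point to what Section 9.5.2 states. It does not remove the point, because that section names the covariate method for the primary outcome and BDNF and is silent here.

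Other stronger readings also fail:

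- **A loss of 15–35% as a fact.** That range follows only from assuming r between 0.7 and 0.3. The documents give no r for connectivity.
- **A biased contrast or a spurious site effect.** Under randomisation the unadjusted change contrast is unbiased and its type I error is valid. The imbalance shifts above average to zero over randomisations and are part of the lost precision.
- **The PCC maps share the defect.** Their wording is too loose to show this.
- **Imaging contrasts are the weakest analyses in the trial.** No imaging power is stated, and the moderator interactions of Aim 2c would ordinarily be weaker at the same size.

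It is also fair that change is a natural quantity here, since the plan correlates connectivity change with behavioural change. That supports keeping change scores for that purpose, not for the group comparison.

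**Conclusion.** The point holds in a limited form. As written, the between-network comparisons rest on change scores with no stated baseline covariate, which is inconsistent with the plan's own treatment of the primary outcome and BDNF and less efficient than the available alternative. The direction is secure for any r meaningfully below 1. The size depends on an assumed r and equal variances: from about 5% of precision at r = 0.9 to about 50% at r = 0. If Appendix VIII already includes baseline z in the model, nothing is lost and only the wording of Section 9.5.2 needs attention.

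This concerns a secondary, mechanistic aim. It does not touch the primary test, the sample size or the validity of the randomised comparison. It is worth making because the gain is nearly free.

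**What to change.** - **Section 9.5.2, between-network analysis.** State that groups are compared on the Visit 13 Fisher z for each ROI pair, with treatment group as the factor and the Visit 2 z for that pair as covariate. Regressing change on group plus baseline z is equivalent.
- **Appendix VIII.** Make it consistent, or confirm that it already specifies this.
- **Change scores.** Keep them for description and for the correlations with behavioural change.
- **PCC maps.** State the group-level model. Baseline z differs at every voxel, so adjustment needs software that accepts a voxel-specific covariate. Where that is unavailable, apply the adjustment to the ROI-level connections that Section 9.5.2 already names (PCC with hippocampus, parahippocampal region, LPC and mPFC).

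For the ROI pairs, the cost is a sentence of SAP text and one added regressor, with no new data, visits or participants. The voxelwise maps need somewhat more programming. The change should be fixed before unblinding, so that the choice between change scores and ANCOVA is not left open across several ROI pairs and three group contrasts.
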